## **Study Summary**

### **Title:**

The use of a dynamic compression intramedullary nail for tibiotalocalcaneal arthrodesis

### **Purpose:**

The purpose of this study is to determine the clinical efficacy of a novel dynamic compression intramedullary nail for tibiotalocalcaneal (TTC) arthrodesis.

### **Design**

This is a prospective, single-group study. Patients of UAB who are scheduled to undergo TTC arthrodesis will be screened for eligibility and informed consent will be obtained from those who meet the inclusion/exclusion criteria. Subjects will be assessed pre-operatively and then at several post-operative intervals: 2 weeks, 6 weeks, 12 weeks, 24 weeks, and 1 year. A CT scan will be obtained at the 24-weeks interval.

### **Population:**

The study population will consist of up to 30 subjects from UAB who meet the following criteria:

#### **Inclusion Criteria:**

- Meets indications for TTC arthrodesis and receives the DynaNail implant
- Able to understand the requirements of the study, provide a written consent, and willing to comply with the study protocol
- 18 years of age or older

#### **Exclusion Criteria:**

- Investigator determines that the subject is unlikely to comply with the requirements of the study
- Non-English speaker
- Blind
- Illiterate
- Prisoner

### **Outcome Parameters:**

The following information will be collected at study visits:

- Pain using a 100mm Visual Analog Scale (VAS)
- Short form-36 (SF-36)
- Foot and Ankle Ability Measure (FAAM)

## Purpose of the Study:

The purpose of this study is to determine the clinical efficacy of a novel dynamic compression intramedullary nail for tibiotalocalcaneal (TTC) arthrodesis.

## Background & Significance:

Arthritis of both the ankle (tibiotalar) and subtalar (talocalcaneal) joints (Figure 1) is debilitating due to severe pain and loss of function. Unfortunately, the only conservative treatment option is bracing which often fails to relieve pain and the decision to perform surgery is subsequently made. The only surgical option is to perform a fusion (arthrodesis) of both of these hindfoot joints. This procedure is called a tibiotalocalcaneal arthrodesis and involves preparing these joint surfaces by removing the arthritic cartilage until healthy bleeding bone is obtained, allowing the body to “glue” the bones together. TTC arthrodesis is an orthopedic procedure with nearly 30,000 operations performed annually at a cost of approximately \$32,000 per procedure [1]. Non-union is the most severe complication, with reported non-union rates as high as 50% [2-5]. Patients with conditions such as diabetes mellitus and Charcot neuroarthropathy and behaviors such as chronic smoking are at a particularly high risk for non-union [3, 6-10]. If a non-union is left untreated, irreversible damage can occur and revision arthrodesis or amputation are the only remaining treatment options.

[figure not shown]

Figure 1. (left) IM nail fixation of TTC joints. (middle) Non-union 16 weeks post static IM nail fixation. (right) Bony fusion 6 weeks post dynamic sustained compression nail fixation.

However, the body can take several months to a year to achieve union and therefore, internal support is mandatory. This is typically performed with an intramedullary (IM) nail (Figure 1) that is inserted through the bottom of the foot, traverses both joints, and is fixed to the shin bone (tibia). Additionally, in order to help the body achieve union faster, compression of the bone surfaces together is performed at the time of surgery. This is analogous to putting a clamp across two pieces of wood that have been glued together until the glue dries. With traditional intramedullary nails for a tibiotalocalcaneal arthrodesis, compression is manually obtained at the time of surgery [11]. However, this initial compression is lost soon after surgery as bone settling or resorption occurs at the joint spaces [12, 13]. If even 1 mm of bone resorption occurs at the joint interface, implanted nails loosen and as a result require a second procedure to provide additional compression [7, 8]. Therefore, it would be ideal to have a medical device that both stabilizes the tibiotalocalcaneal arthrodesis and provides dynamic compression to accommodate the bone resorption that occurs after surgery [14].

The DynaNail is a tibiotalocalcaneal arthrodesis intramedullary nail that allows for compression at the time of surgery and has a nitinol (pseudoelastic memory metal [15-17]) element that is

stretched to a lengthened state during the surgical procedure and slowly contracts to its resting state after the surgical procedure to provide dynamic sustained compression while bone resorption is occurring at the ankle and subtalar joints [7]. In addition to dynamic sustained compression, the DynaNail also provides torsional stability and load-sharing capacity absent in traditional IM nails. To date, minimal clinical data is available to evaluate the effects of sustained compression via IM nail on TTC arthrodesis, particularly in high-risk patients with challenging pathologies [11, 18, 19].

This study's immediate impact on human health is the use of a novel medical device to understand how sustained compression influences joint arthrodesis, especially in the presence of bone resorption. By having a more fundamental understanding of the mechanobiology of clinical TTC arthrodesis, this study's longer term impact on human health will be the design of more efficient medical devices that would fuse joints over shorter time periods and in cases of detrimental pathology where non-union would otherwise occur.

#### **Design & Procedures:**

This proposal is a collaborative effort between UAB and MedShape, Inc. This is a prospective investigation to assess the clinical outcomes of patients with a tibiotalocalcaneal arthrodesis with the Dynamic Compression Intramedullary Nail (DynaNail). We are planning on enrolling 30 patients. No placebo control will be used, as there is no other IM nail available capable of providing sustained compression. Additionally, given that many patients receiving this treatment have had prior failed treatments and face poor alternatives such as amputation, using a prior-generation IM nail as a control treatment would be unethical.

#### *Subject Recruitment:*

Patients of UAB with end-stage tibiotalar (ankle) and talocalcaneal (subtalar) joint arthritis from any etiology will be eligible to enroll in the study. In general, tibiotalar and subtalar arthritis is caused by trauma. Traumatic injuries have no predilection for race, religion, cultural background, etc. Therefore, all demographic groups will have access to this study and should be represented.

#### *Selection of Subjects:*

Patients will be identified in the clinic by an attending orthopaedic foot and ankle surgeon or his physician assistant based on clinical exam and radiographic findings. Patients will be screened for eligibility by the research coordinator/ key personnel in close coordination with the surgeon.

The following inclusion criteria will be used:

- Meets indications for TTC arthrodesis and receives the DynaNail implant
- Able to understand the requirements of the study, provide a written consent, and willing to comply with the study protocol
- 18 years of age or older

The following exclusion criteria will be used:

- Investigator determines that the subject is unlikely to comply with the requirements of the study
- Non-English speaker
- Blind
- Illiterate

- Prisoner
- Pregnant women

*Consent Process:*

Upon determination that a subject is compatible with the eligibility criteria of the protocol, the study will be explained to the subject by the investigator or his/her authorized designee. If the subject indicates interest in participating in the study, the informed consent document will be provided to the patient, since this document provides a comprehensive explanation of the study in lay terms. If the subject continues to show interest, the investigator or his/her authorized designee will thoroughly explain to the subject the required elements of informed consent and all aspects of the study (i.e., inclusion/exclusion criteria, risks, benefits and alternatives to the study, etc.). The subject will receive a copy of the study consent form and the signed and dated original copy will be retained in the subject's study file. After the patient leaves the clinic building, the attending surgeon will be available to answer questions by phone. The process of obtaining informed consent will be in accordance with all applicable regulatory requirements (Federal Register Vol. 48, No. 17, 1982, pp 8951-2).

*Pre-operative Questionnaire:*

After informed consent, the patients will be asked to complete the following patient reported outcomes questionnaires: 100mm VAS for pain, Short form-36 (SF-36), and the Foot and Ankle Ability Measure (FAAM). They will then be scheduled for surgery in a routine fashion. These questionnaires are being done for this research only.

*Surgery:*

The following surgical procedure is standard of care. The surgical procedure will involve both tibiotalar and talocalcaneal joint preparation through any approach (lateral, posterior, anterior with sinus tarsi). The use of supplemental bone graft is at the discretion of the treating surgeon but must be documented. The MedShape DynaNail will then be inserted according to the manufacturer's technique. The patient will be placed in a short leg splint and kept non-weight bearing. The patient will be discharged from the hospital when medically ready.

*Follow-Up Visits and Questionnaires:*

The patient will return to clinic for visits at the following intervals after surgery: 2 weeks, 6 weeks, 12 weeks, 24 weeks, and 1 year. At each of these time points, the same patient specific outcome questionnaires will be administered: the 100mm VAS for pain, SF-36, and the FAAM. 3-view X-rays will be taken at each of these visits to assess the amount of travel of the compressive element. At 24 weeks post-op, a CT scan will be obtained to assess healing. Additionally, a radiographic and clinical follow-up form will be filled out at each of the following follow-up visits: 6 weeks, 12 weeks, 24 weeks, and 1 year. At 24 weeks and 1 year post-op, all X-ray images will be de-identified and burned to a CD/DVD, along with CT images at the 24 weeks time point. A summary of interventions and time points, and whether or not they are standard of care, is depicted in Table 1. MedShape will be responsible for payments of all non-standard of care items.

Table 1. Study Intervention Timeline

	Baseline	Surgery	2 weeks PO	6 weeks PO	12 weeks PO	24 weeks PO	1 year PO
Office Visit (with questionnaires*)	SOC	SOC	SOC	SOC	SOC	SOC	SOC
Radiographic and Clinical Follow-Up Form			NS	NS	NS	NS	NS
3 view ankle xray	SOC	SOC	SOC	SOC	SOC	SOC	SOC
CT Scan						SOC	
Image deidentification						NS	NS
*VAS, FAAM, SF-36							
SOC - Standard of Care, NS - Not Standard of Care							

### **Subject Withdrawal:**

Subjects may voluntarily withdraw from the study upon request. The investigator may withdraw a participant if he/she is unable or unwilling to participate in study follow-ups. The reason for withdrawal will be documented by research staff. Subjects that fail to schedule surgery, cancel surgery, or that do not receive the DynaNail will be considered to be screen failures and will be removed from the study and the study data.

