### **Adverse Events:**

Due to the observational nature of the study, only adverse events (AEs) that are serious, unexpected, and device-related will be recorded. AEs will be collected from the time that the study subject receives the DynaNail implant. All adverse events will be monitored and reported per UAB IRB policies.

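### The rule removing subjects who do not receive the DynaNail can also delete attempted insertions that were abandoned or converted, and so may raise the reported fusion rate

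*Combined protocol and SAP*

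**What the plan says.** The Study Summary gives the aim as to "determine the clinical efficacy of a novel dynamic compression intramedullary nail" and the design as "This is a prospective, single-group study". The Data Analysis & Statistical Considerations section names fusion as the primary outcome but defines no analysis set or denominator.

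Both lists of inclusion criteria contain "Meets indications for TTC arthrodesis and receives the DynaNail implant". Under Selection of Subjects, eligibility, consent and the baseline questionnaires all come first, and only afterwards: "They will then be scheduled for surgery in a routine fashion". Receipt of the nail is therefore an entry criterion that can be known only after the operation.

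The Subject Withdrawal section lists three routes to removal: surgery never scheduled, surgery cancelled, and nail not received. Subjects in the third group, who "do not receive the DynaNail will be considered to be screen failures and will be removed from the study and the study data", are treated like the other two. The same section says "The reason for withdrawal will be documented by research staff", without saying whether a screen failure counts as a withdrawal. Under Adverse Events, "AEs will be collected from the time that the study subject receives the DynaNail implant".

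**The concern.** Subjects who never reach an attempt say nothing about the device, and removing them is reasonable. A subject whose insertion was tried and then given up is different, because the device or the procedure may be the reason for non-receipt. The first two routes already cover patients who never get to surgery, so the third naturally reaches patients who had surgery and left without the nail.

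If any such case occurs and is deleted, the primary result describes completed implantations only. The result of a single-group study is one proportion, so its denominator matters. A reader could not tell how many attempts lie behind the rate, or separate failed attempts from operations that were never scheduled or were cancelled.

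**Working it through.** **Does any section keep an attempted but not implanted subject in the data?**

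- *Inclusion Criteria* (both lists): no. They make receipt a condition of entry.
- *Surgery*: no. It describes insertion of the nail and makes no provision for an insertion that does not succeed.
- *Adverse Events*: no. Collection starts at receipt, and is limited to device-related events that are both serious and unexpected.
- *Data Analysis*: no. There is no all-attempted or all-consented set.
- *Data & Safety Monitoring*, items 2 and 8: partly. Unexpected harm probably related to the device, and unanticipated device effects, are reportable and not restricted to implant recipients. This is a reporting duty; it does not put the subject back into the study data.
- *Privacy, Data Storage & Confidentiality*: enrollment logs are mentioned and might give consented versus implanted counts. Nothing says they record whether insertion was attempted.

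**Direction.** Let x be the number fused with the DynaNail, n the number implanted, and k the number of excluded attempts, none counted as fused with the DynaNail. The reported rate is x/n and the all-attempted rate is x/(n + k). Then

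x/n − x/(n + k) = xk / [n(n + k)] ≥ 0,

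so removal leaves the rate unchanged (k = 0 or x = 0) or raises it.

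**Size.** The only design figure is the 30 subjects. It rests on precedent with no formula inputs, so there is nothing to reproduce, and the point does not depend on it. The values of x and k below are assumptions.

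If 30 are implanted and the attempts come on top:

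| Fused / implanted | k = 1 | k = 2 | k = 3 |
|---|---|---|---|
| 15/30 = 50.0% | 15/31 = 48.4% | 15/32 = 46.9% | 15/33 = 45.5% |
| 24/30 = 80.0% | 24/31 = 77.4% | 24/32 = 75.0% | 24/33 = 72.7% |
| 27/30 = 90.0% | 27/31 = 87.1% | 27/32 = 84.4% | 27/33 = 81.8% |

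The falls run from 1.6 points (50.0 − 48.4) to 8.2 points (90.0 − 81.8).

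The Population section says "The study population will consist of up to 30 subjects from UAB". If failed attempts count within those 30, then 24 fused of 30 attempted (80.0%) would be reported as 24/29 = 82.8%, 24/28 = 85.7% or 24/27 = 88.9% for k = 1, 2 or 3.

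For scale, the exact (Clopper-Pearson) 95% intervals are 31.3 to 68.7% at 15/30, 61.4 to 92.3% at 24/30 and 73.5 to 97.9% at 27/30. Every shifted rate in the table lies inside the interval for its own row.

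**Chance that the issue arises.** With an assumed abandonment rate r per attempt, the chance of at least one case in 30 attempts is 1 − (1 − r)^30. This is 26% at r = 1%, 60% at 3%, 79% at 5% and 96% at 10%. At r = 0 it is zero. The documents give no value for r.

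**The case against.** The strongest reply is that the problem may never occur. No section mentions abandonment or conversion. The section on surgery and device-related risks says the manufacturer knows of no broken compressive element, during or after surgery, and that an element which fails in place leaves an ordinary nail. Such a subject has still received the nail and stays in the data. This stands, but it covers one failure mode and not other reasons for giving up an insertion.

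A second reply is that the study asks how sustained compression affects fusion, which can be observed only in implanted patients. That also stands, and is why fusion among implanted subjects should remain the main figure. It does not justify deleting the attempts.

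A third is that the shifts are smaller than the sampling error. They are, in these illustrations. But the shift goes in one direction, and the confidence interval does not allow for it.

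A reader might infer more than the documents support:

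- *That failed attempts are certain to be deleted.* The wording permits this, but depends on an undefined word; a nail inserted and removed in the same operation could be kept or lost.
- *That harm in a failed attempt would go unreported.* The Data & Safety Monitoring section still makes unexpected, probably device-related harm reportable, and the Adverse Events section refers to the IRB's policies. The gap in the study data is narrow.
- *That the study's conclusion would change.* The plan states no success threshold, so none can be crossed.

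**Conclusion.** The point holds in limited form. The removal rule makes no distinction by reason for non-receipt, and no other section keeps an attempted but not implanted subject in the study data. If such cases count as not fused with the DynaNail, the rule can only leave the reported fusion rate unchanged or raise it.

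The size is unknown and possibly zero. With one to three excluded attempts on top of 30 implanted, and assumed fusion of 50 to 90%, the overstatement would be 1.6 to 8.2 points. These are illustrations, not bounds; more attempts would give a larger shift. Severity is low to moderate: the remedy is cheap and the rule works in the device's favor, but nothing in the documents shows that a case will arise.

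**What to change.** 1. In Subject Withdrawal, limit screen failure and removal to subjects in whom DynaNail insertion was never attempted. Define attempted by one operative-note event fixed in advance (for example, the nail introduced into the canal), and receipt as the nail in place at the end of surgery.
2. Keep attempted but not implanted subjects in the study data from the operative note, with the reason and any adverse event of the kind the Adverse Events section already records, collected from the attempt and not from receipt. Note beside both lists of inclusion criteria that receipt defines the main analysis set and is not a reason to delete attempted cases.
3. Report consented, attempted and implanted counts with reasons. State in Population, Design & Procedures and Data Analysis that the 30 means implanted subjects, so that no implanted cases are lost to the new count.
4. In Data Analysis, keep fusion among implanted subjects as the main figure and show beside it the number fused with the DynaNail divided by all attempted. Fusion obtained with another device is not credited.

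The cost is wording changes, a little data entry from operative notes, and one added figure that may be slightly lower than the main one. Converted subjects need no study follow-up for this figure, so there are no extra sponsor-paid forms, image handling or stipends. If no attempt is abandoned, the two figures coincide and the report can say so.

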### **Adverse Events:**

Due to the observational nature of the study, only adverse events (AEs) that are serious, unexpected, and device-related will be recorded. AEs will be collected from the time that the study subject receives the DynaNail implant. All adverse events will be monitored and reported per UAB IRB policies.

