**Data & Safety Monitoring:**

As this is a minimal risk study, no data and safety monitoring (DSMB) will be used. Data will be managed using Microsoft Excel. Monitoring of study conduct and safety data will be conducted on an ongoing basis by Sponsor.

The following will be reported within 10 calendar days, except when 24-hour reporting is specified:

1. Information that indicates a change to the risks of potential benefits of the human research:
  - a. An interim analysis, safety monitoring report, publication in the literature, or revised investigator brochure that indicates an increase in the frequency or magnitude of a given harm, uncovers a new risk, or provides more information about the benefits of the human research.
  - b. Change in FDA labeling or withdrawal of the device from the market.
  - c. Protocol deviation that harmed participants or indicates participants might be at increased risk of harm. If the protocol deviation was made in order to eliminate an apparent immediate hazard to a participant, the PI must submit the information within 24 hours.
  - d. Complaint of a participant that indicates participants or others might be at increased risk of harm or at risk of a new harm.
2. Any adverse event experienced by a participant or other individual, which is both unexpected and at least probably related to the human research device.
  - a. A harm is “unexpected” when its specificity and severity are not accurately reflected in the consent document.
  - b. A harm is “at least probably related” if the research device more likely than not caused the harm.
  - c. Timeline Exception: If the unexpected and at least probably related harm is death of a research subject, the PI must report the information within 24 hours.
3. Finding of Non-Compliance or Allegation of Non-Compliance.

4. Protocol Deviations: Failure to follow the protocol due to the action or inaction of the investigator or research staff. Exception – If the protocol deviation was taken in order to eliminate an apparent immediate hazard to a participant, the PI must report the information within 24 hours.
5. Breach of confidentiality: must be reported within 24 hours.
6. Change to protocol taken without prior IRB review to eliminate an apparent immediate hazard to a participant: must be reported within 24 hours.
7. Complaint of a participant that cannot be resolved by the research team.

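### Adverse events are recorded only if serious, unexpected and device-related, so some events the plan makes reportable are not recordable and known device harms are not counted in the AE record

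*Combined protocol and SAP*

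**What the plan says.** Three statements in the combined protocol and SAP bear on this.

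- **Recording.** The Adverse Events section gives the observational nature of the study as its reason and says that "only adverse events (AEs) that are serious, unexpected, and device-related will be recorded". Collection starts when the subject receives the implant. The section closes with "All adverse events will be monitored and reported per UAB IRB policies".
- **Reporting.** Data & Safety Monitoring introduces its list with "The following will be reported within 10 calendar days, except when 24-hour reporting is specified". Item 2 of that list is "Any adverse event experienced by a participant or other individual, which is both unexpected and at least probably related to the human research device". A harm is unexpected when its "specificity and severity are not accurately reflected in the consent document". It is at least probably related when the device more likely than not caused it.
- **Oversight.** The same section says that "no data and safety monitoring (DSMB) will be used" and gives ongoing monitoring of study conduct and safety data to the sponsor.

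**The concern.** The recording rule is narrower than the reporting rule. A record normally holds at least everything that must be reported from it. Here, staff who follow the Adverse Events section exactly would make no AE entry for a class of event that Data & Safety Monitoring obliges them to report within 10 calendar days.

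The recording rule also makes unexpectedness a condition of entry. A device harm that the consent document already describes is then left out however serious it is. With one arm, up to 30 subjects and no DSMB, the sponsor's own monitoring is the safety oversight that the plan describes, and the AE record would give it no count of known device harms. A zero for such a harm would reflect the recording rule and would say nothing about the device.

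**Working it through.** The plan gives no figure to reproduce. The check sets the two rules side by side.

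**Inputs.** The recording rule (Adverse Events) requires serious AND unexpected AND device-related. The reporting rule (Data & Safety Monitoring, item 2) requires unexpected AND at least probably device-related.

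**Step 1: classes of event.** Three yes/no attributes give 2 × 2 × 2 = 8 classes. The 4 classes that are not device-related are neither recorded nor reportable under item 2. For the other 4, taking the event to be related under both wordings:

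| Device-related event | Recorded as an AE? | Reportable under item 2? |
|---|---|---|
| Serious, unexpected | Yes | Yes |
| Non-serious, unexpected | No | Yes |
| Serious, expected | No | No |
| Non-serious, expected | No | No |

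**Step 2: the mismatch.** Recorded: 1 of 4. Reportable: 2 of 4. Reportable but not recorded: 2 − 1 = 1 class, the non-serious unexpected events. These are counts of logical classes. They do not say what share of events would be affected.

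**Step 3: expected events.** Both expected classes are absent from the AE record, including the serious one. Item 2 does not ask for them to be reported, so this is a gap in the record and not a conflict between the two rules.

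**Step 4: relatedness.** The Adverse Events section does not define device-related, whereas item 2 uses a more-likely-than-not standard. If the first were applied more strictly than the second, even a serious unexpected event could be reportable and not recorded. The text does not settle this.

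**Step 5: is there another route into the AE record?** None is described. Item 8 of the same list requires reporting of unanticipated adverse device effects, but it is also a reporting duty and does not reach expected harms. X-rays at each postoperative visit follow the travel of the compressive element, and the 24-week CT assesses healing, so element travel and non-union can be seen outside the AE record. A radiographic and clinical follow-up form is completed at several visits, but its content is not shown.

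**The case against.** The strongest reply is that the recording rule is deliberate. The surgery is described as standard of care, the study as minimal risk, and the primary outcome is fusion. The plan has no safety endpoint and promises no AE rate, so it cannot be faulted for failing to deliver one. The sponsor monitors safety data throughout, and a report sent to the IRB leaves a trace even without an AE entry.

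Much of this stands. It makes the omission of expected events a weakness of design and not an error. It does not touch the seriousness mismatch: an observational design may justify limiting expedited reports, but it does not explain recording less than must be reported.

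A reader might infer three stronger things that the documents do not support.

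- **That safety data would be lost.** The rules show only that events fall outside the AE record. IRB reports, images or the follow-up form may hold them. Which harms count as expected depends on the consent document, which was not available for this review.
- **That the plan contradicts its own duty to report information that "indicates an increase in the frequency or magnitude of a given harm".** Item 1a attaches that duty to particular sources: an interim analysis, a safety monitoring report, the literature or a revised brochure. It does not require the study's AE record to produce frequencies, and some of those sources are external. A safety monitoring report drawn from this record would lack counts of known harms, but that is a limitation and not a contradiction.
- **That the Adverse Events section contradicts itself in its last sentence.** "All adverse events will be monitored and reported per UAB IRB policies" may mean all events as just defined, or all events covered by IRB policies that are not shown. It is ambiguous. The narrow reading leaves the gap in place, and the broad reading conflicts with the recording rule, so rewording is needed either way.

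**Conclusion.** The point holds and should be fixed. Confidence is high that one class of event, non-serious, unexpected and device-related, is reportable within 10 calendar days but not recordable as an AE. This rests on two sentences of the plan and on no assumed rate. Confidence is equally high that the stated rule keeps expected device-related events, serious ones included, out of the AE record.

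Confidence is low to moderate about how much information would be lost in practice, because the consent document and the follow-up form were not available. The documents give no rates for device harms other than non-union, so no number of affected events can be estimated. Nothing here affects the validity of the fusion outcome or the questionnaire comparisons.

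**What to change.** Amend the Adverse Events section and align it with item 2 under Data & Safety Monitoring:

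1. Record all device-related adverse events, whatever their seriousness or expectedness, from receipt of the implant.
2. Use one definition of device-related in both sections.
3. Note seriousness and expectedness on each entry, and use them as filters for IRB reporting only where the Data & Safety Monitoring list applies them. Item 2 does not apply seriousness.
4. Reword the last sentence of the Adverse Events section to say which events it covers.
5. Report each type of device-related event as n/N with an exact 95% confidence interval. For scale, 0 of 30 gives a two-sided upper limit of 1 − 0.025^(1/30) = 11.6%. That limit can be claimed only for events that the rule allows to be recorded.

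Before adding any data item, check what the radiographic and clinical follow-up form already collects. The cost is one amended paragraph, possibly a few items on an existing form, and slightly more data entry for up to 30 subjects who already attend five postoperative visits.

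Separate editorial item: the text on follow-up visits says that this form "will be filled out at each of the following follow-up visits: 6 weeks, 12 weeks, 24 weeks, and 1 year", which is four visits. Table 1 marks it at five, adding 2 weeks. The two should be reconciled.
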